#### 4.1.2 Secondary endpoints

The feasibility of treatment in a pre-operative setting will be assessed as the number (percent) of patients whose radical prostatectomy was performed on schedule after 4 doses of xentuzumab. Any reasons for delay post-4 cycles will be tabulated.

The safety and tolerability of xentuzumab administered in the pre-prostatectomy setting will be examined through treatment-related adverse events scored using NCI-CTCAE v5.0. These results will be tabulated.

#### 4.1.3 Research/translational endpoints producing single values

Exploratory analyses will be conducted using various statistical tests as appropriate for the data type. These include, but are not limited to, the following.

For endpoints which produce a single value PRE/POST xentuzumab (e.g. circulating biomarkers such as insulin, PSA, PMBC immunotypes; IGF bioactivity; exploratory tissue biomarkers) paired t-tests or Wilcoxon rank sum tests will be used to assess the significance of differences pre and post treatment. Which test will be used will be determined by the results of the Shapiro-Wilk test for normal distribution. For unpaired data, either unpaired t-tests or the Mann-Whitney U test will be used, again depending on results of the Shapiro-Wilk test for normal distribution. These results will be presented and analysed as for primary endpoint markers and as shown in WINGMEN\_DataDefinitions&Tables Section 5. Results will be displayed as either the mean (and standard deviation), or median (with lower and upper quartiles).

Relationships between many of these variables may be assessed for correlation. The Pearson correlation coefficient  $r$  will be used where two sets of raw data show a linear relationship with one another. If the

relationship is monotonic (i.e. non-linear) the Spearman's rank test (correlation coefficient  $\rho$ ) will be used to analyse correlation between ranked data.

We had planned to assess changes in on-study serum IGF-1, previously reported to rise in patients on xentuzumab reflecting hypothalamic-pituitary axis response to blockade of pituitary IGF-1R [6]. However, on-treatment serum IGF-1 values fell in WINGMEN trial subjects, and we found this was due to interference by xentuzumab in the IGF-1R assay used in the Biochemistry laboratory of the John Radcliffe Hospital.

Other research endpoints (e.g. RNA-seq, metabolomics) will generate larger datasets and will be handled using the methods described below.

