14 STATISTICAL ANALYSIS PLAN

Change in phospho-AKT (or downstream target) and phospho-IGF-1R immunoreactive score before and after treatment will be assessed using the Wilcoxon matched pairs signed rank test. Changes in PSA and other IHC markers including Ki67 index, IGF-1R, RRM2, CD31 and immune markers CD4, CD8, PD-L1, FoxP3 will be assessed using a paired samples t-test or a Wilcoxon matched pairs signed rank test if normality assumptions are not satisfied.

The severity of adverse events (AE) will be graded using the National Cancer Institute Common Terminology Criteria for Adverse Events (NCI CTCAE) version 5.0. Adverse events will be summarised; highest grade per patient AE summaries will be presented, according to whether the AEs are considered treatment-related or not, and over time.

A detailed statistical analysis plan will be written and will be finalised before any analysis is undertaken. The analysis plan will be written in accordance with current Standard Operating Procedures.

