- RNA will be extracted from unstained FFPE sections of diagnostic biopsy and in-theatre prostate biopsy cores, initially using freshly cut sections of the two first trial patients identified in Section 3.4, for transcriptional profiling. RNA will be stored in a designated -80°C freezer. If RNA yield and quality are sufficient for sequencing, RNA will be extracted from FFPE sections of the remaining cases and stored at -80°C as above. If RNA yield is insufficient, we will re-review each biopsy with [name] to decide whether we can cut additional sections from some/all of the cases. RNA will be sent on dry ice to Azenta for quality control and sequencing as described in WINGMEN\_DataDefinitions&Tables Section 5.2.2. Final analysis will be performed when RNA-seq data have been accrued from all evaluable trial subjects (i.e. those with sufficient tumour in the diagnostic biopsy to allow within patient comparison with RNA extracted from prostate cancer cores post-xentuzumab).
- Mutation panel screening and TPMRSS2-ERG FISH will be performed on sections of radical prostatectomies as single batches after the samples from the last patient have been collected.
- Phospho-proteomic profiling: fresh frozen punch biopsies taken from unfixed prostatectomies are stored in the Oxford Radcliffe Biobank. Given that we have no matched pre-treatment fresh frozen biopsies, we plan to hold analysis of these samples until the other endpoint analyses have been completed. If sufficient funds remain, and if we can access fresh biopsies from Gleason-matched prostatectomies in non-trial patients, we will analyse tumour lysates by Reverse Phase Protein Array (e.g. Institute of Genetics and Cancer in Edinburgh: [www.ed.ac.uk/cancer-centre/facilities/htpu-microarray-services/reverse-phase-protein-arrays](http://www.ed.ac.uk/cancer-centre/facilities/htpu-microarray-services/reverse-phase-protein-arrays)). The analysis will be performed in a single batch after samples from the last patient have been collected.

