## 4 STATISTICAL PRINCIPLES

### 4.1 Statistical Significance and Multiple Testing

*If the analysis is under a conventional (statistical hypothesis testing approach), state the level of statistical significance and the confidence intervals to be reported. Acknowledgement of the issue of multiple testing (if applicable), together with the rationale of the intention to formally or informally adjust for multiplicity. If no adjustment planned this will be stated. State which outcomes will be adjusted for multiplicity (if applicable).*

Initial analysis will assess variables for normal distribution using the Shapiro-Wilk test. All tests will be 2-tailed and  $p \leq 0.05$  will be accepted as statistically significant.

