#### 4.1.1 Primary endpoint analysis

PRE/POST FFPE tissue biopsy sections stained for phospho-IGF-1R and phospho-S6 will be scanned and analysed on the HALO platform. This is a deep-learning convolutional neural network that generates H-Scores, representing the sum of the % tissues staining 0 (negative), 1+, 2+ and 3+ to generate a score range of 0-300. If the staining intensity is not sufficient to define a scoring range for H-Scores, percentage of positively stained cells will be used as output instead. To assess the significance of differences before and after xentuzumab, the PRE/POST HALO scores will be analysed using a paired t-test, or, if the paired differences do not follow a normal distribution, the Wilcoxon matched pairs signed rank test. Phospho-IGF-1R staining patterns will also be assessed by [name], to semi-quantitatively score signal in the plasma membrane, cytoplasm and nucleus. Existing data from our group suggest that nuclear IGF-1R associates with higher stage prostate cancer [3] .

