#### 4.1.5 RNA-seq

RNA-seq data will be analysed by [name] and [name], [name] lab bioinformaticians. Analyses will use R Statistical Software and the RStudio integrated development environment. A matrix of gene counts containing all samples will be generated by the process(es) described in WINGMEN\_DataDefinitions&Tables Section 5.2.2. Genes with low counts will be filtered using the filterByExpression function in the edgeR R package [8]. Differential expression analysis will be completed using widely used software packages such as DESeq2, edgeR, and limma [9, 8, 10]. All packages correct for the effect of library size. DESeq2 models genes using a negative binomial generalised linear model and tests the null hypothesis that there is no differential expression across the two sample groups using a Wald test. edgeR also tests for differential expression by fitting a negative binomial model and uses the exact test to identify differentially expressed genes. Limma fits a gene-wise linear model and uses moderated t-statistics to perform hypothesis testing. The p-values are corrected for multiple testing using the Benjamini-Hochberg (BH) method to produce an adjusted p-value. Results will be considered significant at adjusted p-value  $\leq 0.05$ , meaning that the proportion of false positives expected amongst the differentially expressed genes is 5%. If the signal from differential expression analysis is not strong, an adjusted p-value  $\leq 0.1$  may be used. An unfiltered list of ranked genes will be used for gene set enrichment analysis (GSEA) to identify pathways that are activated or suppressed by xentuzumab [9]. The primary database that will be used for GSEA is the Gene Ontology (GO) terms for Biological Processes (BP) [10] and the analysis will be run using the clusterProfiler R package with BH multiple test correction. Depending on results of other analyses (e.g. PBMC immunoprofiling), we may manually select relevant pathways (e.g. immune pathways) from Gene Ontology Biological Processes [10], KEGG [11, 12], BioCarta [13], WikiPathways [14], Reactome [15], and Hallmarks MSigDB [16]. Results of GSEA analysis will be considered significant at an adjusted p-value  $\leq 0.05$  or, if the expression signal is low,  $\leq 0.1$ .

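### The SAP names unpaired tests for paired PRE/POST exploratory data: Wilcoxon rank sum in section 4.1.3 and the edgeR exact test in section 4.1.5

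*SAP*

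**What the plan says.** SAP section 4.1.3 covers endpoints that give one value before and one value after treatment: circulating markers, PBMC immunotypes, IGF bioactivity and exploratory tissue markers. For these, "paired t-tests or Wilcoxon rank sum tests will be used to assess the significance of differences pre and post treatment", with Shapiro-Wilk deciding between the two tests. The paragraph then continues: "For unpaired data, either unpaired t-tests or the Mann-Whitney U test will be used". It adds: "These results will be presented and analysed as for primary endpoint markers".

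The primary markers are handled in SAP section 4.1.1 with a paired t-test or, "if the paired differences do not follow a normal distribution, the Wilcoxon matched pairs signed rank test". Protocol section 14 assigns PSA, Ki67, IGF-1R, RRM2, CD31 and the immune markers to a "paired samples t-test or a Wilcoxon matched pairs signed rank test if normality assumptions are not satisfied".

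On the normality check, section 4.1.1 refers to the paired differences. The general rule in section 4.1 reads "Initial analysis will assess variables for normal distribution using the Shapiro-Wilk test". Section 4.1.3 does not say which values are tested.

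For RNA-seq, SAP section 3.4.3 defines evaluable patients as "those with sufficient tumour in the diagnostic biopsy to allow within patient comparison with RNA extracted from prostate cancer cores post-xentuzumab". Section 4.1.5 gives DESeq2, edgeR and limma as example packages, describes DESeq2 as comparing two groups of samples, and states that "edgeR also tests for differential expression by fitting a negative binomial model and uses the exact test to identify differentially expressed genes". It states no patient term for any of the three.

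**The concern.** The trial has no control arm, and SAP section 3.1 rests the design on each man being his own control. A test that ignores the pairing leaves between-patient variation in the error term and gives up that advantage.

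An analyst who follows section 4.1.3 to the letter would run an independent-samples test on paired data whenever Shapiro-Wilk rejects, and real effects of xentuzumab could be missed. Under SAP section 1, departures from the plan must be described and justified, so an analyst who does the right thing would have to report it as a deviation. The independent repeat analysis in SAP section 7 covers the primary and key secondary outcomes only, so it would not catch this.

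These endpoints are exploratory, but the SAP's stated aim (section 2) of finding the genes and proteins that IGF regulates depends on them. There is a further consequence for RNA-seq: section 4.1.5 lets the adjusted p-value threshold move from 0.05 to 0.1 if the signal is weak, and ignoring the pairing can itself weaken the signal.

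**Working it through.** **The plan's own figure.** SAP section 3.2 gives 20 pairs (two-tailed) or 16 pairs (one-tailed) for the signed rank test at effect size 0.68, 5% level and 80% power. For normal data the signed rank test has relative efficiency 3/π, so the effective number of pairs is m = n × 3/π, and power comes from a noncentral t with m − 1 degrees of freedom and noncentrality 0.68 × √m.

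- n = 20, two-sided: m = 19.1, noncentrality 0.68 × √19.1 = 2.97, power 80.3%.
- n = 16, one-sided: m = 15.3, noncentrality 0.68 × √15.3 = 2.66, power 81.2%.

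Both figures reproduce. They apply to the primary endpoint; the documents give no sample size for the exploratory endpoints.

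**Why pairing matters.** With equal variances σ² and PRE/POST correlation ρ, the paired difference has variance 2σ²(1 − ρ). An independent-samples test uses 2σ², so its standardised signal shrinks by √(1 − ρ). In t-test terms with 20 pairs, the paired value is 0.68 × √20 = 3.04. At ρ = 0.5 the unpaired value is 3.04 × √0.5 = 2.15.

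**The two tests alone** (20 pairs, normal data, 20,000 simulated trials per setting, two-sided 5%):

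| ρ | Power, signed rank | Power, rank sum | Type I error, rank sum |
|---|---|---|---|
| 0 | 80% | 82% | 5.1% |
| 0.25 | 80% | 73% | 2.3% |
| 0.5 | 80% | 54% | 0.8% |
| 0.7 | 81% | 28% | 0.1% |

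**The rule as written.** The rank sum test is used only when Shapiro-Wilk gives p ≤ 0.05; otherwise the paired t-test is used. Simulating the whole rule is therefore the fair comparison. Inputs:

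- 20 pairs, and a shift of 0.68 SDs of the paired difference, taken from the pIGF-1R planning value as an illustration;
- normal data, or log-normal data with log SD 0.5 or 1, where the shift and correlation apply on the log scale;
- 5,000 to 6,000 simulated trials per setting.

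The correlation and skewness are assumptions. Power at ρ = 0.3 / 0.5 / 0.7:

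| Data | Normality checked on | Rule with signed rank | Rule as written |
|---|---|---|---|
| Normal | paired differences | 81 / 83 / 82% | 81 / 82 / 79% |
| Normal | PRE and POST separately | 81 / 83 / 82% | 81 / 81 / 77% |
| Log SD 0.5 | paired differences | 78 / 77 / 76% | 75 / 69 / 60% |
| Log SD 0.5 | PRE and POST separately | 79 / 78 / 77% | 72 / 60 / 42% |
| Log SD 1 | paired differences | 73 / 72 / 72% | 69 / 56 / 34% |
| Log SD 1 | PRE and POST separately | 74 / 73 / 73% | 70 / 54 / 28% |

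At ρ = 0 there is no loss: with log SD 1 and separate checks, the written rule has 82% power against 76%. With separate checks, the written rule's type I error is 4.6 to 4.9% for normal data and 2.1 / 0.8 / 0.2% for log SD 1. The unstated target of the normality check matters in its own right: at log SD 0.5 and ρ = 0.7 it moves the written rule from 60% to 42%.

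**RNA-seq.** The exact test compares two groups through their count totals and has no place for a patient factor, so it cannot make the comparison that section 3.4.3 intends. An illustration with assumed inputs shows the direction: 20 pairs, a 1.5-fold change, within-patient dispersion 0.1, unadjusted 5% level, and a paired test on log counts standing in for a patient-blocked model. The paired test has about 95% power throughout. The two-group exact test has about 98%, 86%, 50% and 4% when the between-patient SD on the log scale is 0, 0.3, 0.5 and 0.8. These figures do not estimate the loss in this trial.

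**The case against.** The strongest reply is that this is a wording slip the documents already resolve. Section 4.1.3 sets the phrase beside the paired t-test, gives unpaired data its own test and refers back to the primary-endpoint analysis. Sections 4.1.1 and protocol 14 both name the signed rank test. That is a fair reading of intent, and a careful analyst would probably do the right thing. It does not make the named test correct, and it leaves the SAP and the protocol in conflict on named endpoints.

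The cross-reference to the primary analysis also favours checking normality on the differences, where the losses are smaller. The general sentence in section 4.1 points the other way, so both sets are shown above.

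SAP section 1 allows transformation before analysis. If the log-normal data were logged first, they would become the normal case, with a loss of about 1 to 5 points. This reduces the illustrated loss but does not correct the test.

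On RNA-seq, edgeR is one of three example packages, and DESeq2 and limma can both take a patient term. The edgeR reference that the SAP cites concerns multifactor experiments. The companion Data Definitions and Tables document, which the SAP says must be read alongside it, was not available and may state a paired design. These points stand for the missing patient term. They do not rescue the exact test, which the SAP names explicitly.

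**Conclusion.** The concern holds. Section 4.1.3 names an independent-samples test for paired data, probably by mistake, and section 4.1.5 names an edgeR test that cannot carry the intended within-patient comparison.

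For the single-value endpoints, the power lost ranges from about 1 to 5 points with normal data to about 4 to 45 points with strong skewness, over assumed correlations of 0.3 to 0.7 and both readings of the normality check. The loss disappears at zero correlation. It rests on a borrowed effect size and on assumed correlation and skewness, because the documents give none of these for the exploratory endpoints. The RNA-seq loss is left unquantified.

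When PRE and POST are positively correlated the error is conservative: it hides effects and does not create false ones. The primary endpoint test is correctly paired and is not affected.

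**What to change.** In SAP section 4.1.3, replace the rank sum test with the Wilcoxon matched pairs signed rank test for all PRE/POST comparisons, and state that Shapiro-Wilk is applied to the paired differences, as in section 4.1.1.

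In SAP section 4.1.5, replace the edgeR exact test with edgeR's generalised linear model (likelihood-ratio or quasi-likelihood test). State that the design is patient as a blocking factor plus timepoint, whichever package is used, and check that the Data Definitions and Tables document agrees.

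The cost is two sentences, with the same data and software. The patient terms use degrees of freedom: with 20 complete pairs, 40 − (20 + 1) = 19 residual degrees of freedom per gene, against 40 − 2 = 38 without them. Patients with only one usable RNA sample would add nothing to the paired comparison.

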#### 4.1.4 Metabolomics

Metabolomics profiles will be analysed in the laboratory of [name] (Department of Chemistry, Oxford University) using statistical methods described in [6] and presented as in WINGMEN\_DataDefinitions&Tables Figure 4. In brief, univariate statistical analysis will be used to identify significantly deregulated metabolites (defined by  $\geq 2$  fold-change and false discovery rate (FDR) adjusted p-value  $<0.05$ ). Unsupervised multivariate statistical analysis will include principal component analysis (PCA) to visualise global metabolic profiles and identify outliers. Supervised multivariate statistical analysis will be used to model important compound features that differentiate PRE and POST xentuzumab samples, and pathway analysis will use MetaboAnalyst, based on the Kyoto Encyclopedia of Genes and Genomes (KEGG) metabolite library specific to *Homo sapiens*.

#### 4.1.5 RNA-seq

RNA-seq data will be analysed by [name] and [name], [name] lab bioinformaticians. Analyses will use R Statistical Software and the RStudio integrated development environment. A matrix of gene counts containing all samples will be generated by the process(es) described in WINGMEN\_DataDefinitions&Tables Section 5.2.2. Genes with low counts will be filtered using the filterByExpression function in the edgeR R package [8]. Differential expression analysis will be completed using widely used software packages such as DESeq2, edgeR, and limma [9, 8, 10]. All packages correct for the effect of library size. DESeq2 models genes using a negative binomial generalised linear model and tests the null hypothesis that there is no differential expression across the two sample groups using a Wald test. edgeR also tests for differential expression by fitting a negative binomial model and uses the exact test to identify differentially expressed genes. Limma fits a gene-wise linear model and uses moderated t-statistics to perform hypothesis testing. The p-values are corrected for multiple testing using the Benjamini-Hochberg (BH) method to produce an adjusted p-value. Results will be considered significant at adjusted p-value  $\leq 0.05$ , meaning that the proportion of false positives expected amongst the differentially expressed genes is 5%. If the signal from differential expression analysis is not strong, an adjusted p-value  $\leq 0.1$  may be used. An unfiltered list of ranked genes will be used for gene set enrichment analysis (GSEA) to identify pathways that are activated or suppressed by xentuzumab [9]. The primary database that will be used for GSEA is the Gene Ontology (GO) terms for Biological Processes (BP) [10] and the analysis will be run using the clusterProfiler R package with BH multiple test correction. Depending on results of other analyses (e.g. PBMC immunoprofiling), we may manually select relevant pathways (e.g. immune pathways) from Gene Ontology Biological Processes [10], KEGG [11, 12], BioCarta [13], WikiPathways [14], Reactome [15], and Hallmarks MSigDB [16]. Results of GSEA analysis will be considered significant at an adjusted p-value  $\leq 0.05$  or, if the expression signal is low,  $\leq 0.1$ .

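### The RNA-seq and GSEA cutoff may move from adjusted p ≤ 0.05 to ≤ 0.10 when the observed signal is weak, with no defined trigger and the same label of significance

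*SAP*

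**What the plan says.** SAP section 4.1.5 (RNA-seq) sets the multiplicity method: "The p-values are corrected for multiple testing using the Benjamini-Hochberg (BH) method to produce an adjusted p-value". Genes are significant at an adjusted p-value of 0.05 or less, which the SAP explains as "meaning that the proportion of false positives expected amongst the differentially expressed genes is 5" per cent.

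The next sentence opens a second route: "If the signal from differential expression analysis is not strong, an adjusted p-value" of 0.1 or less may be used. The section closes with a parallel rule for pathways: "Results of GSEA analysis will be considered significant at an adjusted p-value" of 0.05 or less or, "if the expression signal is low", 0.1 or less. No number, metric or decision-maker is given for either condition, and section 4.1.5 does not promise to report which cutoff was applied.

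Two other parts of the SAP set a fixed level. Section 4.1 says "All tests will be 2-tailed and" takes p ≤ 0.05 as the level of statistical significance. Section 4.1.4 (Metabolomics), also a large dataset with an FDR rule, requires an FDR-adjusted p-value below 0.05 and at least a two-fold change, with no relaxation.

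**The concern.** For differential expression, whether the signal is strong can only be judged from the results to which the cutoff is applied. The cutoff can therefore be chosen after the gene list at 0.05 has been seen. The GSEA condition refers to the expression signal and not to the number of pathways found, so the dependence is less direct, but it comes from the same data.

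The looser cutoff comes into play when true changes are few or absent. SAP section 2 gives the aim as identifying key IGF-regulated genes and proteins, and section 3.4.4 carries the results into an integrated analysis. A reader who sees *significant* beside a gene or pathway would not know from the label which of the two error levels applies.

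**Working it through.** **Inputs from SAP 4.1.5.** BH adjustment; default level q = 0.05; relaxed level q = 0.10; trigger not defined.

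**Assumed, because the documents do not give them.** 15,000 genes after filtering; 0 to 1,500 truly changed genes; two-sided z-tests with a mean shift of 2.5 to 4 in changed genes; independent tests unless stated. Each setting used 800 to 4,000 simulated datasets.

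**Step 1: the SAP's own figure.** For independent tests, BH at level q gives FDR = π₀ × q, where π₀ is the share of genes that are truly unchanged. With q = 0.05 this is at most 0.05, so the SAP's 5% is right for that cutoff. Simulation agrees: 0.050 with no changed genes, 0.053 with 50, and 0.045 with 1,500 (π₀ = 0.9, and 0.9 × 0.05 = 0.045).

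**Step 2: the relaxed cutoff alone.** The bound becomes 0.10, and 0.10 / 0.05 = 2. This ratio does not depend on the assumed gene count or effect sizes.

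| Truly changed genes | FDR at 0.05 | FDR at 0.10 |
|---|---|---|
| 0 | 0.050 | 0.106 |
| 0, correlated in blocks (rho 0.5) | 0.045 | 0.088 |
| 50 (shift 3) | 0.053 | 0.100 |
| 150 (shift 3) | 0.048 | 0.099 |
| 1,500 (shift 3) | 0.045 | 0.090 |

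When nothing is changed every call is false, so the first two rows are also the chance of at least one false call. With 2,000 independent tests instead of 15,000 that chance was 0.053 and 0.097.

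**Step 3: the two-step rule.** Its overall FDR needs a trigger. Three were tried: relax if there are no hits at 0.05, if there are fewer than 10, or if there are fewer than 50.

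- No changed genes: 0.106 under all three (0.088 with correlation). Any call at 0.05 is also a call at 0.10, so a rule that relaxes whenever there are no hits makes at least one false call exactly when a fixed 0.10 cutoff would.
- 50 changed genes (shift 3): 0.057, 0.095 and 0.100. The switch was used in 5%, 87% and 100% of datasets.
- 500 changed genes (shift 3): the switch was never used, and the FDR stayed at 0.049.

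**Step 4: what lies between 0.05 and 0.10.** A rough estimate of the false calls in that band multiplies the mean number of calls by the FDR at each cutoff and subtracts.

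- 50 changed genes: 8.90 × 0.0995 − 5.49 × 0.0529 = 0.89 − 0.29 = 0.60 false among 8.90 − 5.49 = 3.41 added calls, about 17%.
- 150 changed genes: 45.1 × 0.0992 − 29.4 × 0.0483 = 4.47 − 1.42 = 3.05 false among 45.1 − 29.4 = 15.7 added calls, about 19%.

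The 10% therefore describes the whole list up to 0.10; the added band is less reliable than that. GSEA was not simulated. Its nominal bound doubles in the same way, but gene sets overlap, so the independent-test figures are only a guide there.

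**The case against.** The strongest reply is that this is exploratory work, openly planned. SAP sections 3.4.3 and 6.5 treat RNA-seq as a tertiary endpoint. Section 1 says the plan is not meant to curtail exploratory analysis. The option to relax is disclosed in advance, and an FDR of 10% is a legitimate level for discovery in a trial of 20 to 30 patients, where missed signals also matter. Section 5.6.3.4 adds a cross-check by two bioinformaticians and checks on known IGF-regulated genes.

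Most of this stands, and it limits the importance of the point. It does not supply a rule. Saying that a threshold may move, without saying when, does not pre-specify it, and the cross-checks test execution without settling which cutoff applies. Had 0.10 been fixed in advance, there would be no objection of this kind.

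Three stronger readings are tempting, and the documents do not support them.

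- **That the SAP's 5% statement is false.** It is attached only to the 0.05 cutoff, where it is correct. The SAP does not claim 5% for calls made at 0.10.
- **That the rule as a whole doubles the FDR.** The nominal bound doubles where the switch is used. The overall rate depends on the trigger and can stay close to 5%.
- **That the gene cutoff carries through to the pathways.** GSEA takes the full ranked gene list, so the gene-level cutoff does not feed into it. The pathway cutoff is relaxed separately.

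**Conclusion.** The concern holds as a modest point about an exploratory analysis. Section 4.1.5 permits a cutoff that depends on the results, has no stated trigger and uses one label for two error levels. It also departs, without a reason, from the fixed levels in sections 4.1 and 4.1.4.

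The factor of two in the nominal bound is exact. The range of about 5% to 10% for the two-step rule, and the no-effect figure of about 10%, rest on the assumed gene count, effect sizes, triggers and independence; with block-correlated genes the no-effect figure was 8.8%. No single error rate can be given for the rule as written, because the trigger is missing. The companion data definitions and tables document was not available for review, but section 4.1.5 does not refer to it for the cutoff.

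The primary endpoint, the secondary endpoints and the safety analysis are not affected.

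**What to change.** In SAP section 4.1.5, make an adjusted p-value of 0.05 or less the only threshold for *significant*, for both differential expression and GSEA, and delete the two conditional allowances. List items with adjusted p-values above 0.05 and up to 0.10 separately as *suggestive (FDR 10%)*, noting that the 10% refers to the whole list up to 0.10 and not to that band alone. Report adjusted p-values for all genes and gene sets.

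This takes a sentence or two and no new analysis. No discovery information is lost; the cost is that fewer items carry the label significant. If the team prefers the looser level, fixing 0.10 in advance and stating it would also remove the dependence on the result.

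The change does not settle two other open choices in the same section: the software ("Differential expression analysis will be completed using widely used software packages such as DESeq2, edgeR, and limma") and the manual selection of pathways in light of other results.
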